2.9 Gantt chart for the trial

A Gantt chart for the trial can be found in Appendix 7.1

3 Ethics

Ethical approval will be sought through the NHS IRAS, following proportionate review.

3.1 Informed consent and the right to withdraw

Participants will be provided with a detailed information sheet describing the study and what will be required of them. They will have at least a week to read the information sheet before consenting to participate and will have the opportunity to speak with a member of the research team if they have any questions or concerns.

3.2 Risk and adverse events

Group singing is a popular and frequently occurring activity and we have come across no documented instances of harm arising from this. Our previous research into the benefits and effects of singing for various groups of people, including people with COPD, mental health problems and older people, has found that the activity of singing in a group has often offered support in times of physical and emotional distress. However, we also acknowledge that people with COPD constitute a group liable to experience health problems which may be exacerbated at any time and due to outside causes. Therefore, we will ensure that all those responsible for running the groups, and especially facilitators, are trained in how to prevent, be alert to and respond to the potential for health issues within this group. For example, they will suggest that participants only engage in activities which they feel comfortable with and reassure them that nothing is compulsory. At least one individual trained in first aid will be present. The venues selected will comply with health and safety legislation and will be disability compliant. There are some contraindications to some of the tests to be administered and these will be addressed through screening participants prior to undertaking the tests (see above section 2.6).

3.3 Vulnerability

We will only be recruiting those who are able to provide informed consent and so will ensure that all recruiters are able to assess capacity as set out in the Mental Capacity Act 2005 and Good Clinical Practice guidelines. We will ensure that explanations of the nature of the project are made clear and are understood. No pressure will be placed on individuals to participate nor will inducements be used. GPs will be involved in identifying and writing to patients for whom the intervention is suitable, which will provide confidence for participants that those involved can be trusted. No indication will be given that the singing intervention will lead to improvements in COPD. Care will be taken to ensure that respondents do not feel overburdened by the demands of the research in terms of data collection.

3.4 Anonymity and confidentiality

We will collect personal data in order to link these to outcomes. We will ensure that all such information is stored safely during the course of the project in accordance with data protection legislation, and that it is destroyed following completion of the project. We will ensure that only researchers have access to the data and that questionnaires are anonymised through the use of coding. No individually identifiable information will be used in any reports resulting from the research.

3.5 Demoralisation of the control group

One issue that may arise in the trial given the nature of the intervention, is that participants randomised to the control arm may feel disappointed having hope to take part in singing. We will ensure at recruitment that all participants are aware of this possibility, understand the need for a control group in the study and consent given those conditions. We will however provide participants in the control group with the opportunity to take part in group singing after the end of the final data gathering session in the trial. In our experience, people who have engaged in a number of singing for health and wellbeing research projects run by the De Haan Centre have generally wanted singing groups to continue after the research phase, and have found a variety of ways to sustain the group, through raising funds or making personal contributions to the cost. We anticipate that this will happen with this study too, and that the existing groups will be able to welcome new members from the control group after the trial.

4. Project Timetable

4.1 Monthly activities on the project

- June onwards 2018 – Formulate study protocol & develop database
- October 2018 onwards – pre-recruitment publicity – target 120 expressions of interest, with the aim of 100 participants formally consenting.
- December 2018 – Ethics application submitted
- March 2019 – Ethics approved
- April 2019-June 2019 – Recruitment to project
- May-June 2019 – Taster sessions
- July 2019 – Consenting and baseline assessments
- August 2019 – Randomisation and letters to participants
- September - November 2019 – Ten weeks singing intervention
- November - December 2019 – Post-intervention assessments
- December - February 2020 – Post-intervention period
- February - March 2020 – Follow-up assessments and interviews
- April - May 2020 – Data analysis
- May - July 2020 – Writing of papers for peer-reviewed journals
- July 2020 – Publication/Dissemination

4.2 Detailed timetable for assessments and the singing intervention

PLEASE NOTE: Sessions are proposed to start at the beginning of September 2019, to ensure that 10 sessions can be run before the middle of November. This will allow the post-intervention assessments to happen in November-December 2019. Easter 2020 is April 12.

May 2019

6 May bank holiday

- 13 Taster session
- 20 Taster session
- 27 May bank holiday

June 2019

- 3 Taster session
- 10 Taster session
- 17 Taster session
- 24 Taster session

July 2019

- 1 Consent and baseline assessments
- 8 Baseline assessments
- 15 Baseline assessments
- 22 Baseline assessments

August 2019

Randomisation and letters out to participants

September 2019

- 2 Session 1
- 9 Session 2
- 16 Session 3
- 23 Session 4
- 30 Session 5

October 2019

- 7 Session 6
- 14 Session 7
- 21 Session 8
- 28 Session 9

November 2019

- 4 Session 10
- 11 Start of follow-up assessments / and three-month break until mid-February

18 Follow-up assessments

25 Follow-up assessments

December

2 Follow-up assessments

9 End of follow-up assessments

16 Christmas break

23

30

January 2020

6

13

20

27

February 2020

3

10

17 Start of follow-up assessments

24 Follow-up assessments

March 2020

2 Follow-up assessments

9 Follow-up assessments

16 End of follow-up assessments

23 Data inputting and cleaning

30 Data inputting and cleaning

April-November 2020

Analysis, report writing, feedback to participants, publications

5. Project Finance

Core funding is provided by Oak Foundation and will be used as outlined below. Further support through staffing is provided by Canterbury Christ Church University, University of Kent and Medway Community Healthcare. The total cost of the trial is estimated to be £75K including contributions in kind (research staff, administration, university services etc.).

A letter from the funder confirming funds is attached to the IRAS application

Research support (e.g. £300 trial registration, Additional support for assessments)	2,000
Delivery of the intervention 14 sessions x 2 = 28 @ £250	7,000
Assessments (University of Kent) 100 participants x 3 assessments @ £50 each	15,000
Travel/subsistence/meetings	2,000
Materials/publicity	2,000
Contingencies	2,000
Total	30,000

6. References

7.2 Text for recruitment publicity

This will be the basis for professionally designed posters, flyers and advertisements

Do you have difficulties with breathing due to COPD (chronic obstructive pulmonary disease)?

Have you already taken part in Pulmonary Rehabilitation?

Would you be willing to participate in a new research trial to study whether group singing can help to improve breathing?

Medway Community Healthcare Respiratory Team is collaborating with researchers at Canterbury and Christ Church University and the University of Kent in an important new project.

Throughout the UK more and more singing groups have been established for people with respiratory illness. The British Lung Foundation promote 'Singing for Lung Health' groups. Further research is needed, however, to measure possible benefits and understand more fully how singing can help with breathing difficulties.

The study will be a controlled trial, and we are looking for 100 participants, half of whom would join a weekly singing group for ten weeks and half would act as a comparison and not be involved in singing. After the project finishes, participants in the comparison condition will be offered the opportunity to join a singing group.

The singing groups will start in the autumn of 2019 and run for ten weeks.

For further details and to register your interest in taking part, please ring [name], Sidney De Haan Research Centre for Arts and Health on [name] or email her on [contact]

For further details of the De Haan Centre's work on singing and health, please visit:

<https://www.canterbury.ac.uk/health-and-wellbeing/sidney-de-haan-research-centre/sidney-de-haan-research-centre.aspx>

7.5 Letter to participant GP

Sidney De Haan Research Centre for Arts and Health
[name]
Folkestone
[name]

Dear Dr. _____

Singing and COPD: A pilot randomised controlled trial

I am writing with the permission of your patient _____ to inform you that he/she is participating in a randomised trial to assess the effects of regular group singing for people with chronic obstructive pulmonary disease.

Recruitment for this trial took place through the Respiratory Team at Medway Community Healthcare.

I attach the patient information sheet for this project, for your information.

If you have any questions regarding this trial, I should be very pleased to hear from you.

Yours sincerely

[name]
Chief Investigator
[contact]
[contact]

7.6 Participant personal information questionnaire

Participant personal information questionnaire

Name _____

Age _____

Address

Name and address of your GP _____

1. What is your sex? Please circle: Male Female

2. What is your marital status? Please circle:

Single/Unmarried

Married

Same-sex civil partnership

Separated but still legally married or legally in civil partnership

Divorced

Widow/widower (including from civil partnerships)

3. How would you describe your national identity? Please circle:

British

English

Northern Irish

Scottish

Welsh

Another Nationality – Please describe here: _____

4. What is your ethnic group?

Choose one section from A to E, then circle one to best describe your ethnic group or background

A. White

English/Welsh/Scottish/Northern Irish/British

Irish

Gypsy or Irish Traveller

Another white background

B. Mixed/multiple ethnic groups

White and Black Caribbean

White and Black African

White and Asian

Another mixed/multiple ethnic group

C. Asian/Asian British

Indian

Pakistani

Bangladeshi

Chinese

Another Asian background

D. Black/African/Caribbean/ Black British

African

Caribbean

Another Black/African/Caribbean/ Black British

E. Another ethnic group

Arab

Another ethnic background

5. Have you received a formal diagnosis of COPD? Yes No

**6. Have you undertaken pulmonary rehabilitation
in the last THREE months?** Yes No

7. If yes, how many sessions did you attend? _____ sessions

8. How would you describe your level of COPD currently?

Mild

Moderate

Severe

Very severe

**9. Have you experienced any significant worsening
of your COPD over the last THREE months?** Yes No

10. Are you affected by other health conditions? Yes No

9. If yes, please describe here:

7.7 MRC Breathlessness Scale

Grade	Description of breathlessness
Grade 0	I only get breathless with strenuous exercise
Grade 1	I get short of breath when hurrying on level ground or walking up a slight hill
Grade 2	On level ground, I walk slower than people of the same age because of breathlessness, or I have to stop for breath when walking at my own pace on the level
Grade 3	I stop for breath after walking about 100 yards or after a few minutes on level ground
Grade 4	I am too breathless to leave the house or I am breathless when dressing

7.8 COPD Assessment Test

The COPD Assessment Test (CAT)

<http://www.catestonline.org/>

This questionnaire is designed to measure the impact COPD (Chronic Obstructive Pulmonary Disease) has on wellbeing and daily life. It can also identify difficulties experienced due to other lung conditions like asthma.

For each item below, circle the number that best describes you currently. Be sure to only select one response for each question.

	I never cough	0	1	2	3	4	5	6	I cough all the time
1	I have no phelgm (mucus) in my chest at all	0	1	2	3	4	5	6	My chest is completely full of phelgm (mucus)
2	My chest does not feel tight at all	0	1	2	3	4	5	6	My chest feels very tight
3	When I walk up a hill or one flight of stairs I am not breathless	0	1	2	3	4	5	6	When I walk up a hill or one flight of stairs I am very breathless
4	I am not limited doing any activities at home	0	1	2	3	4	5	6	I am very limited doing activities at home
5	I am confident leaving my home despite my lung condition	0	1	2	3	4	5	6	I am not at all confident leaving my home because of my lung condition
6	I sleep soundly	0	1	2	3	4	5	6	I don't sleep soundly because of my lung condition
7	I have lots of energy	0	1	2	3	4	5	6	I have no energy at all

7.9 PHQ-9

Over the last 2 weeks, how often have you been bothered by any of the following problems?	Not at all	Several days	More than half the days	Nearly every day
1 Little interest or pleasure in doing things	0	1	2	3
2 Feeling down, depressed, or hopeless	0	1	2	3
3 Trouble falling or staying asleep, or sleeping too much	0	1	2	3
4 Feeling tired or having little energy	0	1	2	3
5 Poor appetite or overeating	0	1	2	3
6 Feeling bad about yourself — or that you are a failure or have let yourself or your family down	0	1	2	3
7 Trouble concentrating on things, such as reading the newspaper or watching television	0	1	2	3
8 Moving or speaking so slowly that other people could have noticed? Or the opposite — being so fidgety or restless that you have been moving around a lot more than usual	0	1	2	3
9 Thoughts that you would be better off dead or of hurting yourself in some way	0	1	2	3

7.10 GAD-7

Over the last 2 weeks, how often have you been bothered by any of the following problems?		Not at all	Several days	More than half the days	Nearly every day
1	Feeling nervous, anxious or on edge	0	1	2	3
2	Not being able to stop or control worrying	0	1	2	3
3	Worrying too much about different things	0	1	2	3
4	Trouble relaxing	0	1	2	3
5	Being so restless that it is hard to sit still	0	1	2	3
6	Becoming easily annoyed or irritable	0	1	2	3
7	Feeling afraid as if something awful might happen	0	1	2	3

A12 – GAD7 total score

7.11 SF-36 v2

This survey asks for your views about your health, how you feel and how well you are able to do your usual activities. Answer every question by checking the appropriate response. There are no right or wrong answers. If you are unsure about how to answer a question, please give the best answer you can.

Your Health in General

1. In general, would you say your health is:

Excellent	Very good	Good	Fair	Poor
-----------	-----------	------	------	------

2. Compared to one year ago, how would you rate your health in general now?

Much better than one year ago	Somewhat better than one year ago	About the same as a year ago	Somewhat worse than a year ago	Much worse now than a year ago
-------------------------------	-----------------------------------	------------------------------	--------------------------------	--------------------------------

3. The following questions are about activities you might do during a typical day. Does your health now limit you in these activities? If so, how much?

	Yes, limited a lot	Yes, limited a little	No, not limited at all
Vigorous activities, such as running, lifting heavy objects, participating in vigorous sports			
Moderate activities, such as moving a table, pushing a vacuum cleaner, bowling or playing golf			
Lifting or carrying groceries			
Climbing several flights of stairs			
Bending, kneeling or stooping			
Walking more than a mile			
Walking several hundred yards			
Walking one hundred yards			
Bathing or dressing yourself			

4. During the past 4 weeks, how much of the time have you had any of the following problems with your work or other regular daily activities as a result of your physical health?

	All of the time	Most of the time	Some of the time	A little of the time	None of the time
Cut down on the amount of time you spend on work or other activities					
Accomplished less than you would like					

Were limited in the kind of work or other activities					
Had difficult performing the work or other activities (for example, it took extra effort)					

5. During the past 4 weeks, how much of the time have you had any of the following problems with your work or other regular daily activities as a result of any emotional problems (such as feeling depressed or anxious)?

	All of the time	Most of the time	Some of the time	A little of the time	None of the time
Cut down on the amount of time you spend on work or other activities					
Accomplished less than you would like					
Did work or other activities less carefully than usual .					

6. During the past 4 weeks, to what extent has your physical health or emotional problems interfered with your normal social activities with family, friends, neighbours or groups?

Not at all	Slightly	Moderately	Quite a bit	Extremely
------------	----------	------------	-------------	-----------

7. How much bodily pain have you had during the **past 4 weeks**?

None	Very mild	Mild	Moderate	Severe	Very severe
------	-----------	------	----------	--------	-------------

8. During the past 4 weeks, how much did pain interfere with your normal work (including both work outside the home and housework)?

Not at all	A little bit	Moderately	Quite a bit	Extremely
------------	--------------	------------	-------------	-----------

9. These questions are about how you feel and how things have been with you with the **past 4 weeks**. For each question, please give the one answer that comes closest to the way you have been feeling. How much of the time during the **past 4 weeks**...

	All of the time	Most of the time	Some of the time	A little of the time	None of the time
Did you feel full of life?					
Have you been very nervous?					
Have you felt so down in the dumps that nothing could cheer you up?					
Have you felt calm and peaceful?					

Did you have a lot of energy?					
Have you felt downhearted and depressed?					
Did you feel worn out?					
Have you been happy?					
Did you feel tired?					

10. During the past 4 weeks, how much of the time has your physical health or emotional problems interfered with your social activities (like visiting friends, relatives etc.)?

All of the time	Most of the time	Some of the time	A little of the time	None of the time
-----------------	------------------	------------------	----------------------	------------------

11. How TRUE or FALSE is each of the following statements for you?

	Definitely true	Mostly true	Don't know	Mostly false	Definitely false
I seem to get sick a little easier than other people					
I am as healthy as anybody I know					
I expect my health to get worse					
My health is excellent					

THANK YOU FOR COMPLETING THESE QUESTIONS!

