- SF-36 v2, Physical health related quality of life and Mental health related quality of life (Jenkinson et al., 1999) (Available from Optum: <http://campaign.optum.com/optum-outcomes/what-we-do/health-surveys/sf-36v2-health-survey.html>)
- Generalised anxiety disorder (as assessed by GAD-7) (Spitzer, et al., 2006)
- Depression (as assessed by PHQ-9) (Kroenke, et al., 2001)
- Anxiety (as assessed by GAD-7) (Kroenke, et al., 2002)
- Lung function and patterns of breathing (as assessed by spirometry and SLP – for further details see below)
Functional exercise (as measured by the 6MWT – further details below)
Use of inhalers, consultations with health professionals and hospital admissions

The standardised measures employed in this trial have been chosen based on previous research on singing and COPD, the outcome of recent systematic reviews (Lewis et al., 2016; McNamara et al., 2017, and the latest guidance on the assessment and diagnosis of COPD (NICE, 2018). All questionnaires have been screened and assessed for suitability as ‘patient reported outcome’ measures using the checklist devised by Francis et al. (2016) (see Appendix 7.10).

We are using CAT, GAD-7 and PHQ-9 as these measures are routinely used by the Medway Community Healthcare Respiratory team in the monitoring of responses to pulmonary rehabilitation.

CAT serves as a COPD-specific quality of life measure and is especially suited to being the primary outcome measure for the study. There is also an established ‘minimum clinically importance’ change score of two points (Kon et al., 2014), and this will provide an important criterion against which to judge the outcome of the trial for clinical purposes.

Both GAD-7 and PHQ-9 have established cut-off points for increasing grades of severity on mental health condition, and will serve to assess the extent to which participants in the trial can be regarded as experiencing clinically significant levels of mental health challenge, and whether this changes over the course of the trial for the intervention group relative to the control. It is recognised also that the two mental health scales can be combined to form a single measure of anxiety-depression.

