The SF-36 will also be used as this measure was employed in both Brompton studies (Lord et al., 2010, 2012), and revealed significant changes on the physical health related quality of life scale, with a large effect of approximately 1. The current study will employ the current version 2 of the SF-36 as opposed to the earlier version used in the previous Brompton studies. This is justified as V2 is the most recent version and we will have the benefit of technical support from Optum, the owners of the scale, together with access to the most recently available and appropriate norms for scoring. We assume that scores arising from the earlier and current version would be virtually identical.

The MRC breathlessness scale (nMRC, see Williams, 2017) will be employed as a score of 3 (out of a score range of 0-4) is often used as a criterion for recommending pulmonary rehabilitation (PR). As this trial will target recruitment towards patients who have undergone or who are receiving PR, it is expected that all participants will have an nMRC score of 3 or 4.

Details of spirometry, SLP assessments and the 6MWT parameters are given in section 2.6 below

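### The SF-36v2 form printed in Appendix 7.11 has 35 answerable items, one short of the 36 its name implies

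*Protocol*

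**What the plan says.** Section 2.1 lists among the secondary outcomes "SF-36 v2, Physical health related quality of life and Mental health related quality of life". It justifies the choice by the two earlier Brompton trials, in which the SF-36 "revealed significant changes on the physical health related quality of life scale". It then states: "The current study will employ the current version 2 of the SF-36 as opposed to the earlier version used in the previous Brompton studies". The reasons given are that version 2 is the most recent, that its owner will give technical support, and that the team will have "access to the most recently available and appropriate norms for scoring". On the change of version, the protocol adds: "We assume that scores arising from the earlier and current version would be virtually identical".

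Appendix 7.11 is headed SF-36 v2 and prints the questionnaire as eleven numbered questions. Question 3, on activities limited by health, is a table that includes the row "Climbing several flights of stairs". Section 2.6 has the questionnaire completed at baseline, at the end of the programme and at six months.

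The protocol gives no item count, no list of which items feed which scale, no scoring algorithm and no rule for missing SF-36 items.

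**The concern.** The name SF-36 implies 36 items. If the printed form has fewer, the team would be administering something other than the instrument it names, and a question that was never asked cannot be recovered at analysis. The protocol's reasons for choosing this measure are the owner's norms and continuity with earlier trials, and both presuppose the complete instrument.

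The probable place of the gap adds to the concern. Question 3 asks about physical exertion, where people limited by breathlessness could plausibly show change. A missing row there would touch the physical score, which is the score that section 2.1 cites from the earlier trials.

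**Working it through.** **Step 1: count the items.** The input is the form in Appendix 7.11. Each row or single question that takes its own answer counts as one item.

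| Question | Content | Items |
|---|---|---|
| 1 | General health ("In general, would you say your health is") | 1 |
| 2 | Change over a year ("Compared to one year ago, how would you rate your health in general now") | 1 |
| 3 | Activities limited by health | 9 |
| 4 | Role problems, physical | 4 |
| 5 | Role problems, emotional | 3 |
| 6 | Social activities, extent | 1 |
| 7 | Bodily pain, amount | 1 |
| 8 | Pain interfering with work | 1 |
| 9 | Feelings over four weeks | 9 |
| 10 | Social activities, time | 1 |
| 11 | True/false statements | 4 |

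Total: 1 + 1 + 9 + 4 + 3 + 1 + 1 + 1 + 9 + 1 + 4 = 35. The figure implied by the name is 36, so the shortfall is 36 − 35 = 1. Other ways of counting do not give 36: leaving out question 2 gives 34, and counting numbered questions gives 11.

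**Step 2: where the gap is likely to lie.** The nine rows of question 3 are vigorous activity, moderate activity, groceries, stairs (several flights), bending, three walking distances, and bathing or dressing. Walking is graded in three steps and stairs in one, so a lower stair step is the natural candidate. This is an inference from the pattern of the form. If it is right, the full block has 9 + 1 = 10 activities.

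**Step 3: could the row have been lost in extraction?** The tables for questions 4, 5 and 9 are split in the text, yet show no obvious loss. The question 3 table runs unbroken under one header. Questions 4 and 9 also contain small slips of English that suggest the form was retyped, and a dropped row would fit that. Loss in extraction is therefore unlikely but possible.

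**Step 4: illustrative size.** The assumptions are not in the documents: ten activities, each scored 1 to 3, summed and rescaled linearly to 0–100. Let m be the respondent's mean on the nine printed activities and x the answer to the absent one.

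- Weight of one step on one item: 100/(10 × 2) = 5.0 points with ten items, and 100/(9 × 2) = 5.56 with nine. A one-step improvement on the absent item, worth 5 points, goes unrecorded.
- If the nine-item sum (9 to 27) is put into the ten-item formula, the range is (9 − 10)/20 × 100 = −5 to (27 − 10)/20 × 100 = 85, instead of 0 to 100.
- If the absent item is replaced by m, the score is (m − 1)/2 × 100. The full score is (9m + x − 10)/20 × 100. The difference, full minus replaced, is 5(x − m).
- At m = 2 the difference is −5, 0 or +5 for x = 1, 2 or 3. At m = 1 with x = 3 it is +10, and at m = 3 with x = 1 it is −10.

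These points are on the scale of the activities block. They cannot be carried over to the physical health score that the protocol names as an outcome, because the documents do not say how that score is formed.

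**The case against.** The strongest reply is that this is a transcription slip in an appendix. The protocol says the instrument is available from its owner with technical support, and it does not say that the appendix page, rather than the owner's form, will be handed to participants. If the owner's form is used, nothing is lost. This is fair, and it makes the consequence conditional. It does not remove the point, because Appendix 7.11 is the only version of the form that the protocol fixes.

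The second reply is that the text was read from a PDF and rows can disappear. In the COPD Assessment Test in Appendix 7.8, for example, the first item stands unnumbered above items 1 to 7. This stands as a caveat, weakened by Step 3 of the working.

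The third reply concerns stronger readings that a reader might infer and that the documents do not support:

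- *The physical score cannot be produced.* The protocol states no scoring or missing-item rule, and Step 4 shows that a score from nine activities is arithmetically possible.
- *The missing activity is known.* There is no item list in the documents, so its place and wording are inferred.
- *The trial's result would be biased.* The analysis in section 2.8 compares singing with control. The item is absent in both arms at every visit, so that contrast is not biased by the omission.
- *A planned comparison with earlier trials fails.* Those trials motivate the choice of measure, but no formal cross-trial analysis is planned.
- *The physical score is the only outcome on which earlier randomised trials found an effect.* Table 1 of the protocol also reports improvements in anxiety in the 2010 trial and in maximal expiratory pressure in the 2009 trial.

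**Conclusion.** The point holds as a defect in a data-collection form. Appendix 7.11 has 35 items against the 36 implied by its name. If the page is used as printed, one item is missing for every participant at all three assessments. The physical health score would then come from an incomplete instrument, so its use with the owner's norms and its comparability with the earlier trials are not assured.

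The damage is to completeness, comparability and possibly sensitivity on a secondary outcome. The validity of the randomised comparison and the primary outcome are not affected. Under the assumptions of Step 4, replacing the absent item by the respondent's own mean would move the activities-block score by at most 5 points for someone averaging mid-scale, and by at most 10 at the extremes.

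The conclusion rests on three things: that the name gives the item count, that no row was lost in reading the PDF, and that the appendix page is the one administered. The location in question 3 is probable and is not needed for the conclusion. Correction is worthwhile because the loss could not be repaired later.

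**What to change.** Before baseline, replace the page in Appendix 7.11 with the complete licensed SF-36v2 form from its owner, and check it item by item to confirm that all 36 are present. This check works wherever the gap lies. State in section 2.6 that the licensed form is the one participants complete.

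If any data have already been collected on the 35-item form, say so in the report and take the owner's scoring advice before presenting norm-based scores from those data.

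The cost is one replaced questionnaire and a short check. The owner's technical support is already part of the plan, and nothing in the design, the sample size or the primary analysis changes.
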